8.2 DATA QUALITY ASSURANCE

A risk-based approach is used for trial quality management. It is initiated by the assessment of critical data and processes for trial subject protection and reliability of the results as well as identification and assessment of associated risks. An Integrated Quality and Risk Management Plan documents the rationale and strategies for risk management during trial conduct including monitoring approaches, vendor management and other processes focusing on areas of greatest risk.

Continuous risk review and assessment may lead to adjustments in trial conduct, trial design or monitoring approaches.

A quality assurance audit/inspection of this trial may be conducted by the sponsor, sponsor's designees, or by IRB / IEC or by regulatory authorities. The quality assurance auditor will have access to all medical records, the investigator's trial-related files and correspondence, and the informed consent documentation of this clinical trial.

8.3 RECORDS

CRFs for individual subjects will be provided by the sponsor. For drug accountability, refer to [Section 4.1.8](#).

8.3.1 Source documents

In accordance with regulatory requirements, the investigator should prepare and maintain adequate and accurate source documents and trial records for each trial subject that include all observations and other data pertinent to the investigation. Source data as well as reported data should follow the 'ALCOA principles' and be attributable, legible, contemporaneous, original, and accurate. Changes to the data should be traceable (audit trail).

Data reported on the CRF must be consistent with the source data or the discrepancies must be explained.

Before providing any copy of subjects' source documents to the sponsor, the investigator must ensure that all subject identifiers (e.g., subject's name, initials, address, phone number, and social security number) have properly been removed or redacted to ensure subject confidentiality.

If the subject is not compliant with the protocol, any corrective action (e.g. re-training) must be documented in the subject file.

For the CRF, data must be derived from source documents, for example:

- Subject identification: sex, year of birth (in accordance with local laws and regulations)
- Subject participation in the trial (substance, trial number, subject number, date subject was informed)
- Dates of subject's visits, including dispensing of trial medication

Proprietary confidential information © 2019 Boehringer Ingelheim International GmbH or one or more of its affiliated companies

- Medical history (including trial indication and concomitant diseases, if applicable)
- Medication history
- AEs and outcome events (onset date [mandatory], and end date [if available])
- SAEs (onset date [mandatory], and end date [if available])
- Concomitant therapy (start date, changes)
- Originals or copies of laboratory results and other imaging or testing results, with proper documented medical evaluation (in validated electronic format, if available)
- ECG results (original or copies of printouts)
- Completion of subject's participation in the trial (end date; in case of premature discontinuation, document the reason for it, if known)
- Prior to allocation of a subject to a treatment into a clinical trial, there must be documented evidence in the source data (e.g. medical records) that the trial participant meets all inclusion criteria and does not meet any exclusion criteria. The absence of records (either medical records, verbal documented feedback of the subject or testing conducted specific for a protocol) to support inclusion/exclusion criteria does not make the subject eligible for the clinical trial.

8.3.2 Direct access to source data and documents

The investigator /institution will allow site trial-related monitoring, audits, IRB / IEC review and regulatory inspections. Direct access must be provided to the CRF and all source documents/data, including progress notes, copies of laboratory and medical test results, which must be available at all times for review by the Clinical Research Associate, auditor and regulatory inspector (e.g. FDA). They may review all CRFs and informed consents. The accuracy of the data will be verified by direct comparison with the source documents described in [Section 8.3.1](#). The sponsor will also monitor compliance with the protocol and GCP.

8.3.3 Storage period of records

Trial site:

The trial site must retain the source and essential documents (including ISF) according to contract or the local requirements valid at the time of the end of the trial (whatever is longer).

Sponsor:

The sponsor must retain the essential documents according to the sponsor's SOPs.

8.4 EXPEDITED REPORTING OF ADVERSE EVENTS

BI is responsible to fulfil their legal and regulatory reporting obligation in accordance with regulatory requirements.

8.5 STATEMENT OF CONFIDENTIALITY AND SUBJECT PRIVACY

Individual subject data obtained as a result of this trial is considered confidential and disclosure to third parties is prohibited with the exceptions noted in [Section 8.7](#).

Proprietary confidential information © 2019 Boehringer Ingelheim International GmbH or one or more of its affiliated companies

Data protection and data security measures are implemented for the collection, storage and processing of patient data in accordance with the principles 6 and 12 of the WHO GCP handbook.

Personalised treatment data may be given to the subject's personal physician or to other appropriate medical personnel responsible for the subject's welfare. Data generated at the site as a result of the trial need to be available for inspection on request by the participating physicians, the sponsor's representatives, by the IRB / IEC and the regulatory authorities.

8.5.1 Collection, storage and future use of biological samples and corresponding data

Measures are in place to comply with the applicable rules for the collection and future use of biological samples and clinical data, in particular

- Sample and data usage has to be in accordance with the informed consent
- The BI-internal facilities storing biological samples from clinical trial participants are qualified for the storage of biological samples collected in clinical trials.
- An appropriate sample and data management system, incl. audit trail for clinical data and samples to identify and destroy such samples according to ICF is in place
- A fit for the purpose documentation (biomarker proposal, analysis plan and report) ensures compliant usage

Samples and/or data may be transferred to third parties and other countries as specified in the ICF.

8.6 TRIAL MILESTONES

The **start of the trial** is defined as the date of the enrolment of the first subject in the trial.

The **end of the trial** is defined as the 'date of the last visit of the last subject in whole trial' ('Last Subject Completed') or 'end date of the last open AE' or 'date of the last follow-up test' or 'date of an AE has been decided as sufficiently followed-up', whichever is latest.

Early termination of the trial is defined as the premature termination of the trial for any reason before the end of the trial as specified in this protocol.

Temporary halt of the trial is defined as any unplanned interruption of the trial by the sponsor with the intention to resume it.

Suspension of the trial is defined as an interruption of the trial based on a Health Authority request.

The EC/competent authority in each participating EU member state will be notified about the trial milestones according to the laws of each member state.

A final report of the clinical trial data will be written only after all subjects have completed the trial in all countries (EU or non-EU), so that all data can be incorporated and considered in the report.

Proprietary confidential information © 2019 Boehringer Ingelheim International GmbH or one or more of its affiliated companies

The sponsor will submit to the EU database a summary of the final trial results within one year from the end of a clinical trial as a whole, regardless of the country of the last patient (EU or non-EU).

8.7 ADMINISTRATIVE STRUCTURE OF THE TRIAL

The trial is sponsored by Boehringer Ingelheim (BI).

The trial will be conducted

under the supervision of the Principal Investigator. Relevant documentation on the participating (Principal) Investigators (e.g. their curricula vitae) will be filed in the ISF.

The PET procedure will be conducted at

under the supervision of an Investigator.

BI has appointed a Clinical Trial Leader, responsible for coordinating all required trial activities, in order to

- Manage the trial in accordance with applicable regulations and internal SOPs
- Direct the clinical trial team in the preparation, conduct, and reporting of the trial
- ensure appropriate training and information of local clinical trial manager (CTM), Clinical Research Associates, and investigators of participating trial sites

The trial medication will be provided by the

Safety laboratory tests will be performed by the local laboratory of the trial site

Analyses of BI 1467335 concentrations in plasma will be performed at

Analysis of the platelet-enriched plasma will be performed at

On-site monitoring will be performed by BI or a contract research organisation appointed by BI.

Data management and statistical evaluation will be done by BI according to BI SOPs.

Tasks and functions assigned in order to organise, manage, and evaluate the trial are defined according to BI SOPs. A list of responsible persons and relevant local information can be found in the ISF.

10. APPENDICES

Not applicable.

Proprietary confidential information © 2019 Boehringer Ingelheim International GmbH or one or more of its affiliated companies

11. DESCRIPTION OF GLOBAL AMENDMENT(S)

11.1 GLOBAL AMENDMENT 1

Date of amendment	24 June 2019
EudraCT number	2018-003745-41
EU number	
BI Trial number	1386-0022
BI Investigational Medicinal Product	BI 1467335
Title of protocol	A Phase I, open-label, Positron Emission Tomography study in healthy male subjects to explore the inhibition of monoamine oxidase B in the brain after multiple oral doses of BI 1467335 (non-randomized, open-label, parallel-group study)
To be implemented only after approval of the IRB / IEC / Competent Authorities	
To be implemented immediately in order to eliminate hazard – IRB / IEC / Competent Authority to be notified of change with request for approval	
Can be implemented without IRB / IEC / Competent Authority approval as changes involve logistical or administrative aspects only	
Section to be changed	
1. Flow Chart: 3 mg Dose Group2. Flow Chart: 10 Dose Group3. Section 1.3: Rationale for performing the trial4. Section 3.1: Overall trial design and plan5. Section 3.2: Discussion of trial design, including the choice of control group6. Section 5.3.4: Pharmacokinetic-pharmacodynamic relationship7. Section 6.1: Visit Schedule8. Section 8.7: Administrative structure of the trial
Description of change	
1. Flow Chart 3 mg Dose Group: Urine drugs, alcohol breath test and urine nicotine have been amended to improve compliance by performing these tests upon readmission to the site on Day 7 and 14 when the subjects are allowed to leave the clinic. In addition, a minor clarification regarding footnote 2 has been added, which states that predose PK sampling after Day 1 should be collected within 30 min before the following dose.

	
2. Flow Chart 10 mg Dose Group: A minor discrepancy regarding the planned PK time points and EOT time window was corrected. In addition, a minor clarification regarding footnote 2 has been added, which states that predose PK sampling after Day 1 should be collected within 30 min before the following dose.3. Section 1.3: Rationale for performing the trial An additional decision point was included in the trial: the 10 mg dose group will be investigated first and in case no inhibition of MAO-B is seen in this group, further investigation of the 3 mg dose group will not be performed and the study will be considered as complete.4. Section 3.2: Discussion of trial design, including the choice of control group Description of the additional decision point as outlined in bullet point 3.5. Section 3.2: Discussion of trial design, including the choice of control group Description of the additional decision point as outlined in bullet point 3.6. Section 5.3.4: Pharmacodynamic-pharmacodynamic relationship Description of this section was omitted in the previous version, the information that no formal analysis of the relationship is planned was added.7. Section 6.1 Visit schedule Clarification regarding deviation window allowance for ECGs, Vital signs and Safety laboratory has been added.8. Section 8.7: Administrative structure of the trial Laboratories for PK analysis and biomarker analysis have been corrected.
Rationale for change	Following discussion with the Ethics committee, an additional decision point was included in the trial in order to ensure that the minimum number of subjects

Proprietary confidential information © 2019 Boehringer Ingelheim International GmbH or one or more of its affiliated companies

	
are investigated.
 
In addition, correction of discrepancies and minor changes in administrative structure were amended in the context of the amendment.

--	--

Proprietary confidential information © 2019 Boehringer Ingelheim International GmbH or one or more of its affiliated companies

11.2 GLOBAL AMENDMENT 2

Date of amendment	
EudraCT number	
EU number	
BI Trial number	
BI Investigational Medicinal Product(s)	
Title of protocol	
To be implemented only after approval of the IRB / IEC / Competent Authorities	
To be implemented immediately in order to eliminate hazard – IRB / IEC / Competent Authority to be notified of change with request for approval	

## **2. LIST OF ABBREVIATIONS**

Term	Definition / description
ADME	Absorption, distribution, metabolism, and excretion
ADS	Analysis data set
AE	Adverse Event
AESI	Adverse event of special interest
ALT	Alanine aminotransferase
AST	Aspartate aminotransferase
AUC 0-24,N	Area under the concentration-time curve of the analyte in plasma over the time interval from 0 to 24 h
BI	Boehringer Ingelheim
CDR	Clinical Data Repository
C max	Maximum measured concentration of the analyte in plasma
C max,N	Maximum measured concentration of the analyte
CRF	Case report form
CTP	Clinical Trial Protocol
CTR	Clinical Trial Report
CV	Arithmetic coefficient of variation
DNA	Desoxyribonucleic acid
ECG	Electrocardiogram
EDC	Electronic data capture
eCRF	Electronic case report form
gCV	geometric coefficient of variation
gMean	Geometric mean
ICH	International Conference On Harmonisation
iPD	Important protocol deviation
IQRMP	Integrated quality and risk management plan
MAO-B	Monoamine oxidase B

---

Term	Definition / description
MedDRA	Medical Dictionary For Regulatory Activities
NIMP	Non-investigational medicinal product
PD	Pharmacodynamic(s)
PDS	Pharmacodynamic Set
PET	Positron emission tomography
PETS	PET set
PK	Pharmacokinetic(s)
PKS	Pharmacokinetic parameter set
RAGe	Report appendix generator
ROI	Region of interest
SAE	Serious adverse event
SD	Standard Deviation
SOC	System Organ Class
TAC	Time activity curve
TS	Treated set
TSAP	Trial Statistical Analysis Plan
ULN	Upper limit of normal range

### **3. INTRODUCTION**

As per ICH E9 ([1](#)), the purpose of this document is to provide a more technical and detailed elaboration of the principal features of the analysis described in the protocol, and to include detailed procedures for executing the statistical analysis of the primary and secondary variables and other data.

This TSAP assumes familiarity with the Clinical Trial Protocol (CTP), including Protocol Amendments. In particular, the TSAP is based on the planned analysis specification as written in CTP Section 7 “Statistical Methods and Determination of Sample Size”. Therefore, TSAP readers may consult the CTP for more background information on the study, e.g., on study objectives, study design and population, treatments, definition of measurements and variables, planning of sample size, randomization.

Study data (including data entered in the RAVE EDC system and external data provided by suppliers) will be stored in a Clinical Data Repository (CDR).

The statistical analyses will be performed within the validated working environment CARE, including SASTM (current Version 9.4, by SAS Institute Inc., Cary, NC, USA), and a number of SASTM-based tools (e.g., macros for the analyses of AE data or laboratory data; Report Appendix Generator system (RAGe) for compilation/formatting of the CTR appendices).

PK parameters will be calculated by means of noncompartmental analysis using Phoenix WinNonlinTM software (current version Phoenix 6.3 or higher, Certara USA Inc., Princeton, NJ, USA). Outputs for the CTR will be generated using SASTM (current Version 9.4, by SAS Institute Inc., Cary, NC, USA).

#### **4. CHANGES IN THE PLANNED ANALYSIS OF THE STUDY**

All analyses as planned in the CTP will be performed and are described in more detail in this TSAP.

In addition, a pharmacodynamic set (PDS) has been introduced for analysis of MAO-B inhibition in platelet rich plasma.

## **5. ENDPOINTS**

### **5.1 PRIMARY ENDPOINT**

The primary endpoint is measured by PET scans and is defined in Section 2.1.2 of the CTP:

- *% reduction in MAO-B availability upon treatment with BI 1467335 on the last treatment day (Day 28 for the 10 mg dose group and Day 42 for the 3 mg dose group) compared to baseline.*

The % reduction in MAO-B availability refers to the whole brain.

### **5.2 SECONDARY ENDPOINTS**

#### **5.2.1 Key secondary endpoints**

Not applicable.

#### **5.2.2 Secondary endpoints**

**CTP, Section 2.1.3:**

*The following secondary endpoints will be determined:*

- *% reduction in MAO-B availability upon treatment with 10 mg BI 1467335 on Day 14 compared to baseline.*
- *% reduction in MAO-B availability upon treatment with 3 mg BI 1467335 on Day 28 compared to baseline.*
- *MAO-B inhibition in platelet rich plasma at Day 14 (10 mg dose group only), Day 28, and Day 42 (3 mg dose group only) compared to baseline.*
- *$C_{max,N}$  (maximum measured concentration of the analyte) and  $AUC_{0-24,N}$  (area under the concentration-time curve of the analyte over the time interval from 0 to 24 h) on Day 14 (10 mg dose group only), Day 28 and Day 42 (3 mg dose group only).*

The % reduction in MAO-B availability refers to the whole brain.

### **5.3.3 Safety and Tolerability endpoints**

Safety and tolerability of BI 1467335 will be assessed based on parameters defined in Section 2.2.2.2 of the CTP:

- *Adverse events (including clinically relevant findings from the physical examination)*
- *Safety laboratory tests*
- *12-lead ECG*
- *Vital signs (blood pressure, pulse rate)*

#### **5.4.1 Demographic and other baseline characteristics**

The following demographic variables and baseline characteristics will be reported in the eCRF: Sex, ethnicity, race, birth year, age, smoking status, alcohol history, height, weight, relevant medical history and concomitant therapy.

Body mass index will be calculated as weight [kg] / height [m].

## 6. GENERAL ANALYSIS DEFINITIONS

### 6.1 TREATMENTS

For basic study information on treatments to be administered, assignment of treatment groups, and selection of doses, cf. Section 4 of the CTP.

Each subject is planned to be treated daily over a period of 4 or 6 weeks with BI 1467335 film-coated tablets:

Table 6.1: 1 Dosage and treatment schedule

Substance	Formulation	Unit strength	Dosage
BI 1467335	Film-coated tablet	10 mg	2 tablets (5 mg) qd for 28 days
BI 1467335	Film-coated tablet	3 mg	3 tablets (1 mg) qd for 42 days

In addition to the two investigational treatments stated above, the following non-investigational PET tracer will be used:

- PET tracer (NIMP)  
≤ 100 µg [C]-L-deprenyl-D2 as solution for injection for a predose assessment and about 1,5 h after dosing of BI 1467335 on Day 14 (10 mg dose group only), Day 28 and Day 42 (3 mg dose group only).

For statistical analyses of AEs, the following separate analysis phases will be defined for each subject:

Table 6.1: 2 Analysis phases for statistical analysis of AEs

Study analysis phase	Label	Start	End
Screening	Screening	Date of informed consent	Date/time of first administration of BI 1467335
On treatment	BI 1467335	Date/time of first administration of BI 1467335	12:00 a.m. on day after subject's end of study participation date.

In CTR Section 15, AE displays will be presented for the on-treatment phase only.

In CTR Section 15, AE tables, the following totals will be provided in addition:

- "Total on treatment", defined as the total over all on-treatment phases

AEs during the screening phase will be listed in CTR Section 16.2 but not tabulated.

Statistical analyses of safety laboratory tests and vital signs will be conducted with clear differentiation between baseline (cf. [Section 6.7](#)) and on-treatment measurements.

More details on the technical implementation of these analyses are provided in the ADS Plan of this TSAP.

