3. If several actions are indicated at the same time point, the intake of meals will be the last action.
4. Subjects are to be fasted for at least 10 h before sample is taken.
5. Only urine drug, alcohol screening and assessment of urine cotinine to confirm no smoking will be done on Day -1. On Day 7 and Day 14, these assessments will only be performed upon re-admission, in case the subject leaves the unit for the afternoon.
6. End-of-trial (EoTrial) examination to be performed on Day 47-50, EoTrial examination includes physical examination, vital signs, ECG, safety laboratory, recording of AEs and concomitant therapies.
7. For definition of the individual subject's end of trial see [Section 6.2.3](#).
8. Dynamic PET scan will be acquired from 0 to 90 minutes after injection of the PET ligand [¹¹C]-L-deprenyl-D2. In parallel arterial blood samples will be collected continuously for 15 min using an automated blood sampling system at a speed of 5 mL/min. In addition, arterial blood will be drawn manually at several time points during the PET scan.

Proprietary confidential information © 2019 Boehringer Ingelheim International GmbH or one or more of its affiliated companies

9. Subjects will be hospitalized at the clinical trial site from admission on Day -1 to Day 43. On Day 7 and Day 14, subjects will be allowed to leave the unit in the afternoon.
10. AEs and concomitant therapies will be recorded throughout the trial, but will be specifically asked for at the times indicated in the [Flow Chart](#) above.
11. On trial days 28 and 42 subjects will be allowed a light breakfast after safety assessments have been completed.
12. Discharge from trial site after completion of all assessments, including physical examination for confirmation of fitness.
13. Predose PET scan will only take place once subjects have completed all screening procedures (including MRI) and they are considered eligible for study participation.

15. On the days of the PET scans, any PK samples that would need to be taken during the PET scan, can be taken earlier or later, if required. Actual sampling times will be recorded in the CRF.

Proprietary confidential information © 2019 Boehringer Ingelheim International GmbH or one or more of its affiliated companies

DOSE GROUP 10 mg BI 1467335

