		649:30	10:30			x	x	x			
		651:00	12:00			x					
		652:00	13:00	Lunch, 240 mL water intake ³		x					
		655:00	16:00	Snack ³		x					
		657:00	18:00	Dinner ³					x	x	
	29	672:00	09:00	Discharge from trial site and confirmation of fitness ¹²	x				x	x	
3	33-36			End of trial (EoTrial) examination ^{6, 7}	x				x	x	x

1. Subject must be informed and written informed consent obtained prior to starting any screening procedures. Screening procedures include physical examination, check of vital signs, ECG, safety laboratory (including drug, alcohol, nicotine and virus screening), demographics (including determination of body height and weight, BMI, smoking status and alcohol history), relevant medical history, concomitant therapy and review of inclusion/exclusion criteria. In case subject is considered eligible for study participation, an MRI will be conducted as part of the screening procedures.
2. The time is approximate; the procedure is to be performed and completed within a time window of 3 h prior to drug administration. After start of treatment on Day 1, further predose PK blood sampling should be performed within 30 minutes before next scheduled dosing.
3. If several actions are indicated at the same time point, the intake of meals will be the last action.
4. Subjects are to be fasted for at least 10 h before sample is taken.
5. Only urine drug, alcohol screening and assessment of urine cotinine to confirm no smoking will be done at this time point.
6. End-of-trial (EoTrial) examination to be performed on Day 33-36, EoTrial examination includes physical examination, vital signs, ECG, safety laboratory, recording of AEs and concomitant therapies.
7. For definition of the individual subject's end of trial see [Section 6.2.3](#).
8. Dynamic PET scan will be acquired from 0 to 90 minutes after injection of the PET ligand [¹¹C]-L-deprenyl-D2. In parallel arterial blood samples will be collected continuously for 15 min using an automated blood sampling system at a speed of 5 mL/min. In addition, arterial blood will be drawn manually at several time points during the PET scan
9. Subjects will be hospitalized from admission on Day -1 up to Day 29.
10. AEs and concomitant therapies will be recorded throughout the trial, but will be specifically asked for at the times indicated in the [Flow Chart](#) above.
11. On trial days 14 and 28, subjects will be allowed a light breakfast after safety assessments have been completed.

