7.3.4 Safety analyses

Safety will be analysed based on the assessments described in [Section 2.2.2.2](#). All treated subjects (TS, refer to [Section 7.2](#)) will be included in the safety analysis. Safety analyses will be descriptive in nature and based on BI standards. No hypothesis testing is planned.

Proprietary confidential information © 2019 Boehringer Ingelheim International GmbH or one or more of its affiliated companies

For all analyses, the treatment actually administered (= treatment at onset) to the subject will be used (any deviations from the randomised treatment will be discussed in the minutes of the Report Planning Meeting).

Treatments will be compared in a descriptive way. Tabulations of frequencies/proportions will be used to evaluate categorical (qualitative) data, and tabulations of descriptive statistics will be used to analyse continuous (quantitative) data.

Measurements (such as ECG, vital signs, or laboratory parameters) or AEs will be assigned to treatments (see [Section 4.1](#)) based on the actual treatment at the planned time of the measurement or on the recorded time of AE onset (concept of treatment emergent AEs). Therefore, measurements planned or AEs recorded prior to first intake of trial medication will be assigned to the screening period, those between first trial medication intake and end of REP (which corresponds to the patient's individual end of treatment; see [Section 1.2.2](#)) will be assigned to the treatment period. These assignments including the corresponding time intervals will be defined in detail in the TSAP. Note that AEs occurring after the last per protocol contact but entered before final database lock will be reported to Pharmacovigilance only and will not be captured in the trial database.

Additionally, further treatment intervals (analysing treatments) may be defined in the TSAP in order to provide summary statistics for time intervals, such as combined treatments, on-treatment totals, or periods without treatment effects (such as screening and follow-up intervals).

Adverse events will be coded using the Medical Dictionary for Regulatory Activities (MedDRA). Frequency, severity, and causal relationship of AEs will be tabulated by treatment, system organ class, and preferred term. SAEs, AESIs (see [Section 5.2.6.1](#)), and other significant AEs (according to ICH E3) will be listed separately.

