### **7.8.1 Adverse Events**

AEs will be coded with the most recent version of MedDRA.

The analyses of AEs will be descriptive in nature. All analyses of AEs will be based on the number of subjects with AEs and not on the number of AEs.

For analysis, multiple AE occurrence data on the eCRF will be collapsed into one event provided that all of the following applies:

- All AE attributes are identical (lower level term, intensity, action taken, therapy required, seriousness, reason for seriousness, relationship, outcome, AESI)
- The occurrences were time-overlapping or time-adjacent (time-adjacency of two occurrences is given if the second occurrence started at most 1 hour after the first occurrence ended)

The analysis of AEs will be based on the concept of treatment emergent AEs. That means that all AEs will be assigned to screening or on-treatment phases as defined in [Section 6.1](#). AEs will be analysed based on actual treatments, as defined in [Table 6.1: 2](#).

An overall summary of AEs will be presented. This overall summary will comprise summary statistics for the class of other significant AEs according to ICH E3 ([7](#)) and for the class of AESIs.

**CTP, Section 5.2.6.1.4:** “*The following are considered as AESIs:*

- *Hepatic injury*  
*A hepatic injury is defined by the following alterations of hepatic laboratory parameters:*

- *An elevation of AST (aspartate transaminase) and/or ALT (alanine transaminase)  $\geq 3$ -fold ULN combined with an elevation of total bilirubin  $\geq 2$ -fold ULN measured in the same blood sample, or*
- *Aminotransferase (ALT, and/or AST) elevations  $\geq 10$  fold ULN*"

The investigator had to classify on the eCRF whether an observed AE was an AESI or not.

According to ICH E3 (7), AEs classified as "other significant" need to be reported and will include those non-serious and non-significant AEs

- (i) which are marked haematological or other lab abnormalities, or
- (ii) which were reported with "action taken = discontinuation" or "action taken = reduced", or
- (iii) which lead to significant concomitant therapy as identified by the Clinical Monitor/Investigator at a Medical Quality Review Meeting.

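### AE percentages are compared by dose over on-treatment phases about 14 days longer at 3 mg than at 10 mg; at an equal constant AE rate this raises the expected 3 mg figure by up to about 10 to 15 points.

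*SAP*

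**What the plan says.** SAP 6.1, Table 6.1: 2, defines two phases for AE analysis, screening and on treatment. The second starts at "Date/time of first administration of BI 1467335" and ends at "12:00 a.m. on day after subject's end of study participation date". Protocol 1.2.2 has the same intent: the residual effect period is unknown, so AEs up to the end-of-trial examination count as on treatment.

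The end of participation differs by dose. Footnote 6 of the 10 mg Flow Chart reads "End-of-trial (EoTrial) examination to be performed on Day 33-36"; footnote 6 of the 3 mg Flow Chart reads "End-of-trial (EoTrial) examination to be performed on Day 47-50". SAP Table 6.1: 1 gives the 10 mg regimen as "2 tablets (5 mg) qd for 28 days" and the 3 mg regimen as 42 days.

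On the measure, SAP 7.8.1 states: "All analyses of AEs will be based on the number of subjects with AEs and not on the number of AEs". It tabulates these counts by treatment, and SAP 7 takes percentages over all subjects in the set. Table 6.1: 2 has one label for both doses, so the split by dose comes from the by-treatment wording of 7.8.1.

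On the comparison, Protocol 7.3.4 states: "Treatments will be compared in a descriptive way". The same section notes that "further treatment intervals (analysing treatments) may be defined in the TSAP in order to provide summary statistics for time intervals". The SAP defines no such interval.

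**The concern.** The proportion of subjects with at least one AE can only rise as observation lengthens. Here the lower dose is observed for longer, and the extra two weeks are dosing days, because the tail after the last dose is the same in both groups (Day 28 to Day 33-36, and Day 42 to Day 47-50, so 5 to 8 days each). A reader who compares the two columns of the AE table therefore compares dose and follow-up length together. The two pull in opposite directions: if AEs were more frequent at 10 mg, the longer 3 mg phase would offset part of the difference. With five subjects per group and no interval or test beside the percentages, nothing in the table would alert the reader to this.

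**Working it through.** The documents state no AE proportion or rate, so there is no planned figure to reproduce. The check asks how large the gap is when the AE rate is identical in both groups.

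**Inputs**
- Phase length T10 = 33 to 36 days and T3 = 47 to 50 days (SAP Table 6.1: 2 with footnote 6 of each Flow Chart). Mid-window values are 34.5 and 48.5. Allowing for a 09:00 first dose takes 0.375 day off each length and changes little.
- n = 5 per group (Protocol 7.7).
- Assumption: constant daily hazard of a first AE, equal in both groups, scanned over 10 mg proportions from 10% to 80%.

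**Step 1, ratio of observation time.** 47/36 = 1.31; 48.5/34.5 = 1.41; 50/33 = 1.52.

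**Step 2, 3 mg percentage implied by the same hazard.** p3 = 1 − (1 − p10)^(T3/T10).

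| 10 mg | 3 mg, ratio 1.31 | 3 mg, ratio 1.41 | 3 mg, ratio 1.52 |
|---|---|---|---|
| 10% | 12.9% | 13.8% | 14.8% |
| 20% | 25.3% | 26.9% | 28.7% |
| 40% | 48.7% | 51.2% | 53.9% |
| 60% | 69.8% | 72.4% | 75.1% |
| 80% | 87.8% | 89.6% | 91.3% |

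**Step 3, largest gap.** The difference exp(−r·T10) − exp(−r·T3) is greatest at r = ln(T3/T10)/(T3 − T10). At mid-window r = ln(1.406)/14 = 0.0243 per day, giving 56.8% against 69.3%, a gap of 12.5 points. At the window extremes the largest gap is 9.8 points (36 and 47 days) and 15.2 points (33 and 50 days). In subjects this is 5 × 0.098 = 0.5 to 5 × 0.152 = 0.8 of a subject.

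**Step 4, what is seen with five per group.** Exact binomials, mid-window, 40% at 10 mg and 51.2% at 3 mg: the 3 mg percentage is higher with probability 52%, tied 23%, lower 25%. With equal phases at 40% in both groups the figures are 37%, 25% and 37%.

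**Step 5, the same hazard over a common interval.** For 40% over 34.5 days, r = −ln(0.6)/34.5 = 0.0148 per day. Over 28 days, 1 − exp(−0.0148 × 28) = 33.9% in both groups, so the expected gap is zero.

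**Step 6, PET procedures inside that interval.** By 24 h after the Day 28 dose the 10 mg group is scheduled to have had two on-treatment PET and arterial-cannulation days (Days 14 and 28). The 3 mg group has had at most one, because its first on-treatment scan is on Day 28 and Protocol 6.1 lets a scan fall up to 2 days late. Over the full phase each group has two. The common interval therefore equalises dosing days but not PET procedures.

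**The case against.** The unequal duration is an open feature of the design. The 28 and 42 days appear in SAP Table 6.1: 1, directly above the phase definition, and Table 6.1: 2 only carries out Protocol 1.2.2. Protocol 7.3.4 permits further intervals but does not require them, so a reader who infers that the SAP departs from the protocol would be wrong.

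A constant hazard is doubtful. AEs from arterial cannulation and tracer injection follow the PET days, of which both groups have two on treatment, and do not scale with calendar time. AEs that cluster early would also bring the gap towards zero. This stands as a limit on the size. It does not remove the concern, because Protocol 3.2 describes exposure rising over time and inhibition that could accumulate, so the later dosing days cannot be assumed free of events.

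Safety is a further objective with no hypothesis test. The groups are neither randomised nor concurrent, and the 3 mg group is dropped if 10 mg shows no MAO-B inhibition. AE onset times are recorded and individual values listed, so with ten subjects the timing can be read directly. SAP Table 6.3: 1 also names treatment exposure as an output. All of this lowers the stakes. An exposure summary would reveal the imbalance but would not adjust the AE percentages.

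Finally, resting every between-dose statement on the common interval would discard the last 14 days of 3 mg dosing and all later follow-up, and would bring in the PET imbalance of Step 6. That objection stands in full and shapes the fix.

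**Conclusion.** The point holds in a limited form. The AE tables compare cumulative percentages over phases that differ by about 14 days, with no adjustment in the SAP text available. Under an equal constant hazard the expected 3 mg percentage is inflated by at most about 10 to 15 points, depending on where the end-of-trial visits fall; 40% at 10 mg corresponds to 49% to 54% at 3 mg. The direction disfavours seeing a dose-related increase.

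A reader might infer that the lower dose will look worse, or that a dose effect will be hidden or reversed. The documents do not support that. The shift holds in expectation only, is less than one 20-point step with five subjects, and in the 40% example leaves 3 mg tied or lower in 48% of trials. The size rests entirely on the assumed hazard. Nothing here touches the primary endpoint, and the question does not arise if the 3 mg group is not run. It is a modest, directional and cheaply reduced bias in a descriptive safety reading.

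**What to change.** In SAP 6.1 and 7.8.1:

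1. Keep the full-phase AE tables as planned.
2. Beside them print, by dose group, the subject-days on treatment and the number of subjects with an AE per 100 subject-days at risk, counting each subject's days to first AE or to the end of the phase.
3. Add one overall and drug-related AE summary restricted in both groups to first dose through 24 h after the Day 28 dose (planned time 672:00). Footnote it to say that by then the 10 mg group is scheduled to have had two on-treatment PET and arterial-cannulation days and the 3 mg group at most one.
4. State that the between-dose comparison is read from the full-phase and common-interval displays together, not from the common interval alone.

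Repeating the full tables by system organ class and preferred term is not needed with five subjects per group. The cost is one extra analysis interval and a few outputs from data already collected. The drawback is that the common-interval summary leaves out later follow-up and has unequal PET procedures, which is why it supplements the full-phase tables and does not replace them.
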